8. STATISTICAL METHODOLOGY AND STATISTICAL ANALYSES

The intent-to-treat (ITT) analysis of efficacy based on the FAS will be considered as primary. The per-protocol (PP) analysis based on the PPS will be provided as a sensitivity analysis. Safety analysis will be performed for all subjects who had any investigational product dispensed.

Change from baseline in the natural log-transformed psoriatic skin infiltrate thickness/EPB will be determined by subtraction of the baseline assessment from each post-baseline assessment.

The area under the curve (AUC) of the psoriatic skin infiltrate thickness/EPB from Day 1 to Day 19 will be determined using the linear trapezoidal rule. The log AUC will be performed by the natural logarithm of the AUC of the psoriatic skin infiltrate thickness/EPB.

In addition to the model-based analyses described below, all study endpoints will be summarized using descriptive statistics. For binary endpoints, summary statistics including

the numbers and percentages will be presented. For continuous endpoints, descriptive statistics (n, mean, median, standard deviation, minimum, and maximum) will be presented, by each planned measurement time point and treatment group if applicable. Inter-quarter ranges and 95% confidence intervals may be provided where meaningful.

8.1. Analysis of Primary Efficacy Endpoint

The primary endpoint for this study is the change relative to baseline in psoriatic skin infiltrate thickness/EPB at Day 19 [REDACTED] for PF-06763809 in comparison to vehicle. The efficacy assessment of PF-06763809 will be performed for the change from baseline in log of the psoriatic skin infiltrate thickness/EPB on Day 19 using a longitudinal analysis of covariance model, with treatment, visit, treatment by visit interaction as main effects and the log of the psoriatic skin infiltrate thickness/EPB at baseline as covariate. The CS@UN covariance structure will be assumed to adequately model the two within-subject factors (treatment, visit), where the compound symmetric (CS) correlation is for repeated measures from different treatments within each visit and the unstructured (UN) correlation is for longitudinal measures from different visits. If there are convergence issues, alternative covariance structure will be examined and adopted. The point estimate and 95% confidence interval (CI) for the difference in log transformed means at Day 19 visit between treatment groups will be constructed using least square means and appropriate standard errors. The assessment of the primary endpoint will be performed at a two-sided significance level of 0.05.

In addition, a landmark analysis of covariance (ANCOVA) model analysis of the primary endpoint at Day 19 will be performed to examine the robustness of the conclusion drawn from the primary longitudinal analyses. The landmark ANCOVA model will include treatment as the main effect, log-transformed psoriatic skin infiltrate thickness/EPB at baseline as covariate and a random subject effect to account for correlation among repeated measures from different treatments for each subject.

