9.1. Sample Size Determination

The sample size determination is based on the primary endpoint of change relative to baseline in psoriatic skin infiltrate thickness/EPB at Day 19. The log-scale of infiltrate thickness is used for a more stable variability over the assessed efficacy range and a better approximation to normal distribution.

Data from three psoriasis plaque test (PPT) studies conducted at bioskin® GmbH were used to generate the assumption for sample size calculation. In these three studies, the calcipotriene/calcipotriol solution demonstrated 36% - 44% reduction in infiltrate thickness relative to vehicle. The observed within-subject standard deviation (SD) estimates for calcipotriene/calcipotriol solution relative to vehicle ranged from 0.331-0.435. Power analyses were performed for samples sizes of N=15 and N=20 under within-subject SDs of 0.38, 0.435 and 0.5 with 2-sided type-I error rate of 5% and results were summarized in

CCI

A sample size of 15 completers was selected based on the above results and enrollment should ensure approximately 15 completers.

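### The primary longitudinal model fits one log-baseline slope for all visits, which can under-adjust the Day 19 contrast and cost some precision (low priority)

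*SAP*

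**What the plan says.** SAP 8.1, repeated in SAP 4.2 and protocol 9.2.1, specifies a longitudinal covariance model "with treatment, visit, treatment by visit interaction as main effects and the log of the psoriatic skin infiltrate thickness/EPB at baseline as covariate". SAP 6.4 names the baseline covariate but gives no interaction with visit. Read literally, one regression coefficient on log baseline applies at every visit.

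Two other features matter here:

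- The response is a change score. SAP 8 says: "Change from baseline in the natural log-transformed psoriatic skin infiltrate thickness/EPB will be determined by subtraction of the baseline assessment from each post-baseline assessment".
- The covariance is a Kronecker product. Compound symmetry covers the treatments within a visit, and "the unstructured (UN) correlation is for longitudinal measures from different visits".

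Only the Day 19 contrast is tested for the primary endpoint. SAP 8.1 also plans a robustness analysis at Day 19 alone: "The landmark ANCOVA model will include treatment as the main effect, log-transformed psoriatic skin infiltrate thickness/EPB at baseline as covariate". That analysis has its own Day 19 slope, but fills missing values by LOCF (SAP 7), whereas the primary model assumes missing at random without imputation.

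**The concern.** The dependence of change on baseline normally strengthens over time. Shortly after Day 1 a field is still close to where it began, so change depends little on baseline. By Day 19 a field that started thicker has more room to fall, and the slope of change on baseline is more negative. A single slope has to compromise between these visits, and generalised least squares does not weight them equally. If early changes vary less, the early visits dominate.

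The Day 19 contrast, the only one that decides the primary hypothesis, would then be adjusted with a coefficient too close to zero. Fields are randomised within subject, so this does not bias the treatment effect. What is at stake is precision in a trial of about 15 completers.

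**Working it through.** **1. Planning figure.** The power table is redacted, so N=15 can only be checked for consistency. In the earlier studies "the calcipotriene/calcipotriol solution demonstrated 36% - 44% reduction in infiltrate thickness relative to vehicle" (protocol 9.1). The within-subject SDs "ranged from 0.331-0.435", and power was computed "under within-subject SDs of 0.38, 0.435 and 0.5". Take a 36% reduction, so δ = −ln(0.64) = 0.446, with SD 0.435 read as the per-field residual SD, two-sided 5%, and an assumed 80% power:

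n = 2 × 0.435² × (1.960 + 0.842)² / 0.446² = 14.9, which rounds up to 15.

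The standard error of a contrast is 0.435 × √(2/15) = 0.159, and normal-formula power at N=15 is 80.2%. So N=15 is consistent with 80% power, but the target is not visible.

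**2. Where the common slope comes from.** Let S be the visit covariance and β the vector of visit-specific slopes. In large samples the common slope is

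b = (1′S⁻¹β) / (1′S⁻¹1).

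Take two visits with variances a and c and covariance a, so that the second visit adds independent noise to the first (a random walk). Then S⁻¹1 = (1/a, 0): all the weight falls on the first visit and none on the last. With equal variances and equal correlations, all visits weigh the same. With assumed visits at Days 4/8/12/15/19 and random-walk responses, the first visit carries 60% to 98% of the weight and Day 19 about none.

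**3. Effect on the Day 19 contrast.** With complete data the contrast is the difference in mean change minus b times the difference in mean baseline. Its variance is

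(2/N) × [σ² + (b − β₁₉)² × τ²],

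where σ is the Day 19 residual SD and τ the within-subject SD of log baseline. With σ = 0.40 (assumed) and slopes from the random-walk simulations:

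| τ | b | β₁₉ | (b − β₁₉)²τ² | SE ratio by formula | SE ratio simulated |
|---|---|---|---|---|---|
| 0.10 | −0.194 | −0.638 | 0.0020 | 1.006 | 1.014 |
| 0.20 | −0.246 | −0.692 | 0.0080 | 1.025 | 1.032 |
| 0.30 | −0.414 | −0.900 | 0.0213 | 1.064 | 1.068 |

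For example, √(1 + 0.0213/0.16) = 1.064.

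**4. Simulation.** 15 subjects × 6 fields, fitted under the planned covariance, 300 runs per scenario. Assumed: visits at Days 4/8/12/15/19 or 8/15/19; baseline reliability 0.9; regression of Day 19 on baseline 0.3 (0.1 when τ = 0.30). Entries are model SE ratios, common slope over visit-specific slopes:

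| Residual pattern | Visits | τ = 0.10 | τ = 0.20 | τ = 0.30 |
|---|---|---|---|---|
| Random walk | 5 | 1.014 | 1.032 | 1.068 |
| Random linear trend | 5 | 1.002 | 1.037 | 1.071 |
| Constant variance | 5 | 0.998 | 1.002 | 1.009 |
| Random walk | 3 | 1.004 | 1.010 | 1.018 |
| Random linear trend | 3 | 1.012 | 1.029 | 1.042 |
| Constant variance | 3 | 0.998 | 1.000 | 1.003 |

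The common slope kept between 0.125/0.641 = 20% and 0.778/0.902 = 86% of the Day 19 slope. The largest mean error was 0.018 log units, about 2.1 Monte Carlo standard errors (0.147/√300 = 0.0085), which is unremarkable among 18 scenarios. Simulated power differed by about 0 to 5 points.

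**5. Meaning for power.** N=15, 36% reduction, normal formula:

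| SD | No loss | SE +2% | SE +5% | SE +7% |
|---|---|---|---|---|
| 0.38 | 89.6% | 88.4% | 86.5% | 85.2% |
| 0.435 | 80.2% | 78.7% | 76.3% | 74.7% |
| 0.5 | 68.6% | 66.9% | 64.4% | 62.7% |

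The documents do not say whether the planning SDs were baseline-adjusted. If they were not, the table does not describe a shortfall. The interaction would instead be a gain: at SD 0.435, an SE smaller by a factor of 1.05 raises power from 80.2% to 83.9%.

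**The case against.** A common slope is a legitimate specification, and four counter-arguments carry weight.

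- **Baseline is not ignored.** Every response already has baseline subtracted, so a slope near zero gives a valid change-score contrast. This stands. A reader might infer that the Day 19 contrast is left almost unadjusted, but the calculations do not support that. In the five-visit random-walk scenario with τ = 0.30, the empirical SE was 0.165 for a plain change score, 0.146 with the common slope and 0.139 with visit-specific slopes. The common slope thus recovers 0.019/0.026 = 73% of the available gain.
- **The mechanism needs growing variance.** No by-visit variance is given, and protocol 9.1 gives more stable variability as a reason for the log scale. This stands: with constant variance the loss was at most 0.9%.
- **Fields must be comparable** (protocol 3.1 and 4.1). This stands in part. The expected range of six normal values is about 2.53 SD, so τ = 0.10, 0.20 and 0.30 imply a thickest-to-thinnest ratio of about 1.3, 1.7 and 2.1. The last strains the word comparable. But the only visible numerical limit is the 200 µm floor, and fields may lie on up to three plaques, so some spread is possible.
- **The landmark analysis already has a Day 19 slope.** True, but it is a robustness check and handles missing data differently. If it disagreed with the primary model, the disagreement could not be traced to the slope or to LOCF alone.

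A reader might also take the loss to be worth about 25% more subjects, from an SE 12% larger (1.12² = 1.25). That needs τ = 0.30 together with a residual log SD rising from 0.15 to 0.43 over the visits. One corner of a large-sample grid reached 14%, with τ = 0.30, a nearly error-free baseline and a Day 4 visit. The documents give no ground for treating such corners as expected.

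**Conclusion.** The point holds as a low-priority efficiency improvement. The plan fits one baseline slope for all visits. If residual variance grows over visits, that slope comes mainly from the early ones and the Day 19 contrast is under-adjusted. Under the assumed values the Day 19 SE is about 0% to 7% larger than with visit-specific slopes: up to 1.4% at a within-subject baseline log SD of 0.10, about 4% at 0.20 and 7% at 0.30. It is close to 0% with constant variance or closely matched fields. These figures rest on assumed visit days, variance patterns, baseline reliability and baseline-to-Day 19 regression, none of which the documents show.

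Neither the validity of the test nor any visible power figure is contradicted.

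**What to change.** Add the log-baseline-by-visit interaction to the longitudinal model in SAP 8.1 and protocol 9.2.1, and align SAP 4.2, SAP 6.4 and the protocol summary. The Day 19 contrast then uses a Day 19 slope, as the landmark analysis already does, and the two analyses become easier to compare. If one common slope is intended, say so and give the reason.

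The cost is one extra slope per additional visit: four with five visits or two with three, against about (15 − 1) × (6 − 1) = 70 error degrees of freedom. No new data are needed. In some scenarios there is no gain, and the least favourable simulated SE ratio was 0.998, so the downside is negligible. The change must be made before unblinding. Protocol 9 requires an amendment for major changes to the primary analysis, so the sponsor should record whether this one counts as major.

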1.2.4. Calcipotriene/calcipotriol Solution

PF-06763809's anti-psoriatic activity will be benchmarked against that of calcipotriene solution. In a similar designed study, Daivonex[®] solution reduced the skin inflammatory infiltrate by 38% relative to vehicle with a within standard deviation (SD) of 0.435 (data on file; bioskin[®]).

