1.2.5. Betamethasone Solution

PF-06763809's anti-psoriatic activity will be benchmarked against that of betamethasone solution. In a similar designed study, Betnesol[®] solution reduced the skin inflammatory infiltrate by 79% relative to vehicle (data on file; bioskin[®]).

While betamethasone solution is approved for scalp psoriasis, the proposed use being highly limited on other skin surfaces in this study, does not significantly increase the risks (or decrease acceptability of risks) associated with the use of this product. As noted earlier, the SRSD is the approved product label.

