4.1. Inclusion Criteria

Subjects must meet all of the following inclusion criteria to be eligible for enrollment in the study:

1. Healthy female subjects of non-childbearing potential and/or male subjects with psoriasis who, at the time of consent and Screening, are ≥ 18 years. Healthy is defined as no clinically relevant abnormalities identified by a detailed medical history, full physical examination, including blood pressure and pulse rate measurement, 12-lead electrocardiogram (ECG) or clinical laboratory tests, as assessed by the investigator.
2. Female subjects must be of non-childbearing potential to enroll into this study and as such, must meet at least one of the following criteria:
 - a. Achieved postmenopausal status, defined as follows: cessation of regular menses for at least 12 consecutive months with no alternative pathological or physiological cause; **and** have a serum follicle-stimulating hormone (FSH) level confirming the post-menopausal state (with a single repeat permitted if deemed necessary by Investigator);
 - b. Have undergone a documented hysterectomy and/or bilateral oophorectomy;
 - c. Have medically confirmed ovarian failure.

All other female subjects (including female subjects with tubal ligations) are considered to be of childbearing potential.

3. Body mass index (BMI) of ≥ 17.5 and $\leq 35.5 \text{ kg/m}^2$; and a total body weight $> 50 \text{ kg}$ (110 lbs).
4. Evidence of a personally signed and dated informed consent document indicating that the subject has been informed of all pertinent aspects of the study.
5. Subjects who are willing and able to comply with all scheduled visits, treatment plans, laboratory tests, and other study procedures.
6. Subjects with psoriasis vulgaris in a chronic stable phase and with a plaque area of mild to moderate severity sufficient for six treatment fields located in up to three plaque areas.
7. The target lesion(s) should be on the trunk or extremities (excluding palms/soles).
 - a. Psoriatic lesions on the knees or elbows are not to be used as a target lesion.
 - b. Test areas to be treated should have a comparable psoriatic skin infiltrate thickness/EPB of at least $200 \mu\text{m}$.

- c. The visual examination of the skin must be without disease findings unless the investigator considers an abnormality to be irrelevant to the outcome of the clinical trial.

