2.2.2. Secondary Objectives

- *To evaluate the Area Under the Curve (AUC) of psoriatic skin infiltrate thickness/EPB for PF-06763809 compared to vehicle.*
- *To assess the effect of PF-06763809 compared to calcipotriene/calcipotriol solution in the change of psoriatic skin infiltrate thickness/EPB both within and following 18 days of treatment.*
- *To assess the effect of PF-06763809 compared to betamethasone solution in the change of psoriatic skin infiltrate thickness/EPB both within and following 18 days of treatment.*

CCI

- 
- 
- 
- 
- 

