4. HYPOTHESES AND DECISION RULES

4.1. Statistical Hypotheses

This study is designed to show that PF-06763809 has a superior effect against vehicle in the primary endpoint of relative change from baseline in infiltrate thickness at Day 19. The following hypotheses will be formally tested first under a significance level of 5% (two-sided):

- The null hypothesis (H_{01}): PF-06763809 has no greater reduction from baseline in infiltrate thickness at Day 19 than vehicle.
- The alternative hypothesis (H_{11}) is that PF-06763809 has a greater reduction from baseline in infiltrate thickness at Day 19 than vehicle.

If the null hypothesis H_{01} is rejected statistically, then the following hypotheses will be formally tested next under a significance level of 5% (two-sided):

[figure not shown]
- The null hypothesis (H_{02}): PF-06763809 has no greater reduction from baseline in infiltrate thickness at Day 19 than calcipotriene/calcipotriol.
- The alternative hypothesis (H_{12}) is that PF-06763809 has a greater reduction from baseline in infiltrate thickness at Day 19 than calcipotriene/calcipotriol.

[figure not shown]
Data from three psoriasis plaque test (PPT) studies conducted at bioskin® GmbH were used to generate the assumption for sample size calculation. In these three studies, the calcipotriene/calcipotriol solution demonstrated 36% - 44% reduction in infiltrate thickness relative to vehicle. The observed within-subject standard deviation (SD) estimates for calcipotriene/calcipotriol solution relative to vehicle ranged from 0.331-0.435. Power analyses were performed for samples sizes of N=15 and N=20 under within-subject SDs of 0.38, 0.435 and 0.5 with 2-sided type-I error rate of 5% and results were summarized C

CCI

I.

CCI

CC1

A large blacked-out rectangular area representing a redacted section of the document, likely containing sensitive information.

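### Does pooling the betamethasone field into the common error variance spoil the test of PF-06763809 against vehicle?

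*SAP*

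**What the plan says.** SAP 8.1 fits one longitudinal ANCOVA to the change in log infiltrate thickness, with treatment, visit, their interaction and log baseline. Its covariance is CS@UN, "where the compound symmetric (CS) correlation is for repeated measures from different treatments within each visit", and unstructured over visits. Protocol 9.2.1 has the same text. Neither document lists the fields in the model. Each subject receives all six treatments, so the natural reading is six.

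SAP 4.1 tests PF-06763809 against vehicle (H01). If that succeeds, it tests against calcipotriol (H02), where the null is that "PF-06763809 has no greater reduction from baseline in infiltrate thickness at Day 19 than calcipotriene/calcipotriol". Betamethasone appears only as a secondary objective: "To assess the effect of PF-06763809 compared to betamethasone solution in the change of psoriatic skin infiltrate thickness/EPB" (SAP 2.2.2).

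The variance information shown concerns calcipotriol. Protocol 1.2.4 reports that the "solution reduced the skin inflammatory infiltrate by 38% relative to vehicle with a within standard deviation (SD) of 0.435", and SAP 4.1 adds: "The observed within-subject standard deviation (SD) estimates for calcipotriene/calcipotriol solution relative to vehicle ranged from 0.331-0.435". For betamethasone, Protocol 1.2.5 says only that the "solution reduced the skin inflammatory infiltrate by 79% relative to vehicle". The reason given for a common variance is in Protocol 9.1: "The log-scale of infiltrate thickness is used for a more stable variability over the assessed efficacy range".

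**The concern.** Compound symmetry forces one variance on all treatments. A 79% reduction is ln(0.21) = -1.561 on the log scale, against ln(0.62) = -0.478 for 38%, so betamethasone is expected to lie 3.3 times as far from vehicle as calcipotriol. A thin residual band may be read with a larger relative error. If betamethasone's log-scale SD were larger than the rest, the intervals for H01 and H02 would be too wide and the one against betamethasone too narrow; if smaller, the reverse. The landmark ANCOVA states no treatment-specific variance, so its agreement would not test the point. SAP 8.1 allows another covariance structure only for convergence problems. At stake would be the width of the primary interval in a study of 15 subjects, and it seems easy to avoid by leaving betamethasone out of that fit.

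**Working it through.** **Inputs.** From the documents: n = 15, six fields, two-sided 5%, SD 0.435, reductions of 38% and 79%. Inclusion criterion 7b reads "Test areas to be treated should have a comparable psoriatic skin infiltrate thickness/EPB of at least" 200 µm. Assumed: r, the ratio of one field's residual SD to that of the others; model-based standard errors; 69 df for six fields and 55 for five; reading errors of 5, 10 and 20 µm; vehicle fields unchanged.

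**The plan's figure.** The power results are redacted, so 15 completers cannot be checked against a stated power. If 0.435 is the residual SD, the SE of a difference is 0.435 × √(2/15) = 0.159, and a paired test (14 df) has 79.9% power for a 38% reduction. That fits a target near 80%, but this is an inference.

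**Step 1: betamethasone's influence on H01.** With complete data the model's SE differs from the true SE by the factor k = √((5 + r²)/6). Type I error is P(|t| > k × 1.995) on 69 df; power uses the noncentral t with noncentrality 0.478/0.159. For PF against betamethasone, k = √[((5 + r²)/6) / ((1 + r²)/2)].

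| r (betamethasone) | k, H01 | Type I, H01 | Power at 38% | Type I, PF vs betamethasone |
|---|---|---|---|---|
| 0.5 | 0.935 | 6.6% | 87.2% | 2.1% |
| 1 | 1.000 | 5.0% | 84.3% | 5.0% |
| 1.13 | 1.023 | 4.5% | 83.2% | 6.0% |
| 1.46 | 1.090 | 3.3% | 79.6% | 8.7% |
| 2 | 1.225 | 1.7% | 71.3% | 12.7% |

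Without betamethasone, H01 has type I error 5.0% and power 84.1% at every r. Simulations with a baseline covariate agree to within about one point.

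**Step 2: which r is plausible.** A 79% reduction from 200 µm leaves 200 × 0.21 = 42 µm. For reading error s and thickness m, r = √(0.435² − (s/m)² + (s/(0.21m))²)/0.435.

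| s | r at m = 200 µm | r at m = 400 µm |
|---|---|---|
| 5 µm | 1.04 | 1.01 |
| 10 µm | 1.13 | 1.04 |
| 20 µm | 1.46 | 1.13 |

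The value 1.46 needs every field at the entry minimum and a 20 µm error on a 42 µm band. No case reaches 2. Every case gives r above 1, which makes H01 and H02 conservative; the 6.6% at r = 0.5 has no mechanism behind it. If 0.435 is instead the SD of the difference, r at 200 µm runs from 1.07 to 1.81, but power falls only from 98.7% to 96.5%.

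**Step 3: is betamethasone special?** The SDs shown cover calcipotriol relative to vehicle. None is shown for the three PF-06763809 strengths, and this is a first-in-human study. Type I error for H01 when PF fields carry the ratio (pooled variance over true variance, as in Step 1; critical value 2.004 for five fields):

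| Assumption | Six fields | Five fields |
|---|---|---|
| Tested PF field r = 1.46 | k = √(1.189/1.566) = 0.871; 8.7% | k = √(1.226/1.566) = 0.885; 8.2% |
| Tested PF field r = 2 | k = √(1.5/2.5) = 0.775; 12.7% | k = √(1.6/2.5) = 0.800; 11.5% |
| Other two PF strengths r = 0.5 | k = √0.75 = 0.866; 8.9% | k = √0.70 = 0.837; 9.9% |

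Dropping betamethasone barely helps in the first two rows and does harm in the third. The five-field fit holds 5% in Step 1 only because betamethasone alone was allowed to vary.

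**The case for a change.** The strongest reply is that the trade looks lopsided. With equal variances, leaving betamethasone out costs about 0.3 points of power (84.3% against 84.1%). With unequal ones it protects H01 and H02 whatever r is. It would also settle which fields enter the model. For the betamethasone comparison, the common variance could give a type I error of 11.5% at r = 1.81 even under the favourable reading of the SD.

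Part of this stands. The mechanics are right, the field list is not written out, and equal variance is assumed rather than shown. But the protection covers only one of the four fields without a displayed SD. The alternatives also cost something:

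- A paired regression for PF against betamethasone gives a 10% wider interval when variances are equal. It uses only subjects with both values, whereas the planned longitudinal model works under missing at random.
- A paired contrast for H01, which would avoid the common-variance assumption altogether, has 76% simulated power against 83% for the pooled model.
- Even with equal variances, the five-field and six-field verdicts differ in 2.2% of simulated trials.

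The plan is not blind to the matter either. SAP section 8 provides SDs by time point and treatment, so a markedly different betamethasone SD should be visible. SAP 8.1 does not restrict the standard errors to model-based ones.

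**Conclusion.** The concern does not hold. Pooling six randomised fields under one log-scale variance is a defensible choice with a stated rationale, and the documents contain no evidence against it. At a 10 µm reading error and the 200 µm minimum (r = 1.13), the cost to H01 is under one point of power, and its type I error stays below 5%. Effects of practical size need r of roughly 1.5 or more, and no figure in the documents supports such a value. The comparison with betamethasone is more sensitive (6.0% at r = 1.13, 8.7% at 1.46), but it is a secondary objective outside the two formal hypotheses. Whether to pool all fields, drop one, model separate variances or use paired contrasts is a matter of preference with real trade-offs. This conclusion rests on model-based standard errors, complete Day 19 data and assumed ratios; the redacted power results may hold planning data that cannot be seen here.

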6.4. Covariates

Baseline values of psoriatic skin infiltrate thickness/EPB will be included as a covariate in the longitudinal and landmark analysis of covariance (ANCOVA) analysis of the primary endpoint.

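### Both efficacy models use one baseline slope that blends between-subject and within-subject slopes, so the within-subject PF-06763809 contrasts may lose a little precision

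*SAP*

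**What the plan says.** SAP 8.1 analyses the change from baseline in log EPB. The primary longitudinal model has treatment, visit and their interaction, with "the log of the psoriatic skin infiltrate thickness/EPB at baseline as covariate"; correlation is compound symmetric across fields and unstructured across visits (CS@UN). The landmark model at Day 19 has treatment, "log-transformed psoriatic skin infiltrate thickness/EPB at baseline as covariate and a random subject effect to account for correlation" among the six fields. SAP 6.4 says the same for both: "Baseline values of psoriatic skin infiltrate thickness/EPB will be included as a covariate in the longitudinal and landmark analysis of covariance (ANCOVA) analysis". Protocol 9.2.1 matches. No section adds a subject-mean baseline, separates between-subject from within-subject baseline differences, or fits subjects as fixed effects.

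Three design features matter. Protocol 5.1 randomises six treatments to six fields within each subject. Protocol 4.1, criterion 7b, says: "Test areas to be treated should have a comparable psoriatic skin infiltrate thickness/EPB", with a minimum of 200 µm but no numeric tolerance and no upper limit. SAP 8 defines the response as a change score on the log scale.

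**The concern.** A field's log baseline is the subject's mean plus that field's deviation from it. The subject mean cancels from a within-subject contrast, so only the slope on the deviation should adjust it. A single covariate with a random subject effect, or with compound symmetry, also draws its slope from differences between subjects.

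The two slopes could well differ. Fields chosen to be comparable will differ partly through reading error. That error enters the change score with coefficient -1 and pushes the within-subject slope towards -1. Subjects, by contrast, may differ freely above 200 µm. Those differences are more likely to be real and need not predict change in log EPB. The fitted slope would then lie closer to zero than the contrast needs. If instead the between-subject slope is the steeper, the contrast is over-adjusted.

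At stake is some precision for the comparisons with vehicle and with calcipotriol. It arises at a single visit, so it affects the landmark model as well as the primary one.

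**Working it through.** **1. The plan's own figure.** Protocol 9.1: "A sample size of 15 completers was selected based on the above results". SAP 4.1 ran power "under within-subject SDs of 0.38, 0.435 and 0.5 with 2-sided type-I error rate of 5" per cent; SAP 8.1 confirms the level: "The assessment of the primary endpoint will be performed at a two-sided significance level of 0.05". The benchmark is that "the calcipotriene/calcipotriol solution demonstrated 36% - 44% reduction in infiltrate thickness relative to vehicle". The power results are redacted and no target power is visible, so the choice of 15 cannot be reproduced against a stated power. For orientation, a paired t-test (noncentral t, 14 df, noncentrality |ln(1 - reduction)| × √15 / SD of the difference) gives:
- SD 0.435 read as the SD of the paired difference: 95.8% power at a 36% reduction.
- SD 0.435 read as a per-field SD (difference SD 0.435 × √2 = 0.615): 79.9% at a 38% reduction, the figure in Protocol 1.2.4.

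The documents do not say which reading applies.

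**2. What the single slope estimates.** The documents do not give the between-subject SD of log baseline σb, the within-subject SD σw, the correlation ρ between one subject's responses, or the two slopes. All are assumed below. With 6 fields per subject:
- g = 1 + 6ρ/(1 - ρ)
- B = (6σb² + σw²)/g and W = 5σw²
- between-subject weight f = B/(B + W)
- fitted slope = f × between slope + (1 - f) × within slope
- contrast variance, one slope divided by two ≈ [1 + (f × gap)² σw²/σ²] × (1 - 1/69)

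Here gap is the difference between the slopes and σ² the per-field residual variance. The last factor is the price of estimating the within-subject slope.

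Middle case, ρ = 0.5, σb = 0.3, σw = 0.1, gap 1:
- g = 7; B = 0.55/7 = 0.0786; W = 0.05; f = 0.611.
- 0.435 per field (σ² = 0.189): 1 + 0.611² × 0.01/0.189 = 1.0197; × 0.9855 = 1.005, or 0.2% in SE.
- 0.435 for the difference (σ² = 0.0946): 1.0395 × 0.9855 = 1.024, or 1.2% in SE.

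Extreme corner, ρ = 0.2, σb = 0.6, σw = 0.2, gap 1:
- g = 2.5; B = 2.2/2.5 = 0.88; W = 0.2; f = 0.815.
- With σ² = 0.0946: 1.2807 × 0.9855 = 1.26, or 12% in SE.

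**3. Primary model, simulated.** CS@UN, 15 subjects, 6 fields, 4 assumed visits, 500 runs per row. SDs are on the log scale. Retained is the share of true field differences persisting after baseline. SE loss is √(variance ratio) - 1.

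| Subject baseline SD | True field SD | Reading SD | Retained | Subject response SD | Fitted slope | Within slope | Variance ratio | SE loss |
|---|---|---|---|---|---|---|---|---|
| 0.3 | 0.05 | 0.05 | 0.5 | 0.3 | -0.08 | -0.74 | 1.020 | 1.0% |
| 0.3 | 0.10 | 0.10 | 0.5 | 0.3 | -0.26 | -0.75 | 1.056 | 2.7% |
| 0.3 | 0.15 | 0.10 | 0.5 | 0.3 | -0.30 | -0.65 | 1.022 | 1.1% |
| 0.3 | 0.15 | 0.15 | 0 | 0.3 | -0.58 | -1.00 | 1.087 | 4.3% |
| 0.3 | 0.15 | 0.10 | 0.5 | 0.1 | -0.22 | -0.65 | 1.024 | 1.2% |
| 0.3 | 0.15 | 0.15 | 0 | 0.05 | -0.43 | -1.00 | 1.189 | 9.0% |
| 0.4 | 0.20 | 0.10 | 1 | 0.3 | -0.07 | -0.20 | 1.012 | 0.6% |

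In the sixth row the average model-based SE was 10% larger (0.1182 against 0.1075).

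**4. Landmark model, simulated.** REML, 15 × 6, paired SD 0.38, between slope 0, within slope -1, no true field differences:
- subject response SD 0.4: SE 0.8-1.5% larger
- 0.2: 2.4-4% larger, or 2.2% with true field differences of SD 0.1 added
- 0.1: 7.5% larger

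Moving the between slope to -0.25 cut the loss to 0.3-1.9%; at -0.5 the SD ratio was 0.994-1.003, so nothing was gained. Where the between slope was the steeper and the within slope 0, the fitted slope was -0.10 to -0.37, an over-adjustment. With equal slopes the variance ratio was 0.99-1.00. There was no material bias, and type I error was near 5%.

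**5. In subjects.** The single-slope model needs 15 × the variance ratio to match the two-slope model. A variance loss of 2-9% is worth 0.3 to 1.3 subjects; the sixth row gives 15 × 0.189 = 2.8.

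**The case against.** A single baseline covariate is conventional ANCOVA, and with treatments randomised to fields within subject it gives a valid contrast. That stands.

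The case for a large slope gap is also weaker than it may look. Comparable has no numeric tolerance in criterion 7b. Fields may lie on up to three plaques and are recorded by arm, leg or trunk, so real field differences are likely, and if they persist they flatten the within-subject slope. Selection at 200 µm can itself cause regression to the mean between subjects, which narrows the gap. The result is also sensitive to how much subjects differ in response, which the documents do not report. All of this limits the size of the loss; none of it makes the slopes equal.

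In the landmark runs where this was compared, the single-slope model was still more precise than an unadjusted contrast (SD 0.81-0.98 of it), so what is lost is part of the gain from adjustment.

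A reader might infer a definite shortfall in power. The documents do not support one: no target power is visible. With the SD read as that of the paired difference, even a 6.7% larger SE moves power at a 36% reduction only from 98.8% to 97.7% (SD 0.38) or from 95.8% to 93.3% (SD 0.435). With a per-field SD, power is lower and more sensitive.

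Nor does analysing change from baseline remove the issue. Baseline reading error enters the change score with coefficient -1, which is why the within-subject slope matters.

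**Conclusion.** The point holds as a minor matter of efficiency. Both models fit a slope that is partly between-subject, although every PF-06763809 contrast is within subject. If the slopes differ, the standard error is typically about 0-4% larger than the same data allow, rising to about 7-10% if subjects respond nearly alike; an extreme analytic corner reaches 12%. If the slopes are equal, nothing is lost.

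These sizes rest on assumed baseline SDs, slopes, response SDs and, for the primary model, four visits.

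A reader might infer that the contrast is certainly under-adjusted, or that it is biased. Neither follows: the documents give neither slope, the error could go in either direction, and randomisation within subject protects validity.

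**What to change.** In SAP 8.1 and 6.4, and in Protocol 9.2.1, add the subject's mean of the six log baseline values as a second covariate beside the field's own log baseline, in both the longitudinal and the landmark model. Entering the subject mean and the field's deviation from it is equivalent. The treatment contrasts are then adjusted with the within-subject slope, whichever slope is the steeper.

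Specify this before unblinding, since choosing it afterwards would be data-driven. Protocol 9 already requires the SAP to be final by then, and asks for a protocol amendment if a change to the primary analysis is major.

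The cost is one derived variable from data already collected and some wording. It uses one between-subject degree of freedom, takes none from the within-subject contrasts, and loses at most about 1% of precision if the slopes are equal.
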